5.11 Treatment Compliance

Study treatment administration will take place at the study centre and will be administered by the Investigator or designated and trained study centre personnel. The precise date and time

of administrations shall be documented in the CRF. The study will be monitored by a monitor approved by the Sponsor. During these visits, all procedures will be monitored for compliance with the protocol. Source documents will be reviewed and compared with the data entries in the CRFs to ensure consistency.

[e] Spirometry (FEV₁ and FVC) before and 30 minutes and 1 hour after pMDI salbutamol administration. The pre-bronchodilator FEV₁ must be $\geq 40\%$ and $\leq 80\%$ of predicted normal for inclusion.
[f] One measurement at -15 minutes
[g] UK centre only

6.1 Screening (Visit 1)

Written informed consent will be obtained by the Investigator as specified in Section 11.3 prior to any study related procedures being performed.

Patients will be screened to determine eligibility against the inclusion and exclusion criteria between 3 and 14 days before the first dose of study treatment. There are no fasting requirements for the screening visit. Patients must withhold CF therapies prior to screening as defined in Section 5.9.1.

The following assessments will be performed:

- Reversibility test: spirometry before and 30 minutes and 1 hour after salbutamol administration
- Recording of demographic information
- Recording of medical/surgical and disease history
- Recording of prior medications and therapies
- Vital signs (blood pressure and pulse rate)
- Physical examination
- 12-lead ECG
- Blood and urine samples for laboratory safety tests
- Urine pregnancy tests (female patients only)
- Questioning for adverse events

If the patient meets the inclusion criteria and none of the exclusion criteria, they will be instructed to return in 3 to 14 days for Visit 2.

6.2 Visit 2

Patients must withhold short and long acting bronchodilators prior to Visit 2 as defined in Section 5.9.1. Patients should fast from 2 hours pre-dose until 2 hours post-dose (except for water) and other restrictions defined in Section 5.4.2 should be adhered to.

Patients will be evaluated to ascertain if the inclusion and exclusion criteria are still met.

6.2.1 Pre-Dose Assessments

- Confirm that respiratory medications were withheld as required. If not reschedule the visit for within the required window
- Questioning for adverse events
- Concomitant medication check
- Urine pregnancy test (female patients only)
- Nebuliser inhalation training
- 12-lead ECG
- Vital signs (blood pressure and pulse rate)

- Blood sample for pharmacokinetics
- Exhaled breath pH (UK centre only)
- Sputum for rheology and inflammatory mediator measurements
- Spirometry (one measurement at -15 minutes)

Eligible patients will then be randomised and receive a randomisation number.

6.2.2 Study Treatment Administration

Patients will be dosed either RPL554 or placebo using a nebuliser according to randomisation.

6.2.3 Post-Dose Assessments

- 12-lead ECGs at 1, 2, 4 and 8 hours
- Vital signs at 30 minutes and 1, 2, 4, 6 and 8 hours
- Blood samples for pharmacokinetics at 15, 30 minutes and 1, 2, 4, 6, 8 and 24 hours
- Spirometry at 15 and 30 minutes and 1, 2, 4, 6, 8 and 24 hours
- Questioning for adverse events
- Exhaled breath pH at 8 and 24 hours (UK centre only)
- Sputum obtained for rheology and inflammatory mediator measurement at 8 and 24 hours

Patients completing the visit will be instructed to return in 3 to 14 days for Visit 3.

6.3 Visit 3 to 4

Patients must withhold short and long acting bronchodilators prior each visit as defined in Section 5.9.1. Patients should fast from 2 hours pre-dose until 2 hours post-dose (except for water) and other restrictions defined in Section 5.4.2 should be adhered to. The following assessments will be performed:

6.3.1 Pre-Dose Assessments

- Confirm that respiratory medications were withheld as required. If not reschedule the visit for within the required window
- Questioning for adverse events
- Concomitant medication check
- Urine pregnancy test (female patients only)
- 12-lead ECG
- Vital signs (blood pressure and pulse rate)
- Blood sample for pharmacokinetics
- Exhaled breath pH (UK centre only)
- Sputum for rheology and inflammatory mediator measurements

- Spirometry (at -15 minutes), including confirmation that FEV₁ is within 20% of that at Visit 2

6.3.2 Study Treatment Administration

Patients will be dosed either RPL554 or placebo using a nebuliser according to randomisation.

6.3.3 Post-Dose Assessments

- 12-lead ECGs at 1, 2, 4 and 8 hours
- Vital signs at 30 minutes and 1, 2, 4, 6 and 8 hours
- Blood samples for pharmacokinetics at 15, 30 minutes and 1, 2, 4, 6, 8, 12 and 24 hours
- Spirometry at 15 and 30 minutes and 1, 2, 4, 6, 8 and 24 hours
- Questioning for adverse events
- Exhaled breath pH at 8 and 24 hours (UK centre only)
- Sputum obtained for rheology and inflammatory mediator measurement at 8 and 24 hours

Patients completing Visit 3 will be instructed to return in 3 to 14 days for Visit 4. Patients completing Visit 4 will be instructed to return in 3 to 10 days for Visit 5.

6.4 End of Study (Visit 5)

The following will be performed:

- Questioning for adverse events
- Concomitant medication check
- Physical examination
- Blood and urine samples for laboratory safety tests
- Urine pregnancy test (female patients only)

7 STUDY METHODOLOGY

7.1 Demographics, Baseline Characteristics and Eligibility Assessments

Safety assessments (laboratory safety assessments, vital signs, 12-lead ECG and physical examination) will be performed at screening (Visit 1) as described in Section 7.4.2 to Section 7.4.5 as part of the eligibility assessment.

7.1.1 Demographic Variables

Demographic variables, including date of birth, sex, height, weight, BMI (weight [kg]/height [m]²), race and smoking status will be collected at screening (Visit 1).

7.1.2 Medical/Surgical and Disease History

Active medical conditions and all surgeries will be recorded at screening (Visit 1). Disease history, including date of diagnosis of CF and the specific CF mutations will also be recorded.

7.1.3 Reversibility Test

A reversibility test in response to salbutamol will be performed at screening (Visit 1). Spirometry (FEV₁ and FVC) will be performed before and after (at 30 minutes and 1 hour) two puffs of salbutamol administered using a pressurised metered dose inhaler will be performed and recorded. The pre-brochodilator FEV₁ must be $\geq 40\%$ and $\leq 80\%$ of predicted normal for inclusion. The reversibility response is not an eligibility measure.

At all three timepoints, three technically acceptable measurements should be made and recorded in the CRF. Spirometry assessments may be repeated up to eight times to obtain three acceptable readings according to American Thoracic Society ATS guidelines (Miller, 2005). The highest reading from each assessment will be used for calculation of predicted values and increase from baseline. GLI Quanjer, 2012 will be used as a reference for predicted normal values.

7.1.4 Screening Laboratory Eligibility Assessments

Laboratory safety assessments will be performed as described in Section 7.4.2.

Unscheduled and/or repeat testing may be performed at the discretion of the Investigator.

7.1.5 Prior and Concomitant Medications and Therapies

Prior respiratory therapies and medications taken in the last 3 months will be recorded at screening (Visit 1) and concomitant use during the study recorded as described in Section 5.9.1.

Other prior medications taken in the last 3 months will be separately recorded at screening (Visit 1) and concomitant use during the study recorded as described in Section 5.9.2.

7.1.6 Eligibility Check

Patients will be confirmed as eligible according to the inclusion and exclusion criteria from assessments made at screening (Visit 1) with a final check of all results pre-dose at Visit 2.

7.2 Pharmacodynamic Assessments

7.2.1 Pulmonary Function Tests

Spirometry assessments (FEV₁ and FVC) will be made at the following timepoints at Visit 2 to Visit 4: pre-dose (at -15 minutes), 15 and 30 minutes and 1, 2, 4, 6, 8 and 24 hours post-dose in accordance with ATS/European Respiratory Society (ERS) guidelines (Miller, 2005). At all timepoints, three technically acceptable measurements should be made and recorded in the CRF. Spirometry assessments may be repeated up to eight times to obtain three acceptable readings according to ATS guidelines (Miller, 2005). The highest FEV₁ and FVC readings from each assessment will be used for analysis even if the FEV₁ and FVC values come from two different forced exhalations.

7.2.2 Sputum Measurements

Sputum samples will be taken pre-dose and at 8 and 24 hours post-dose at Visit 2 to Visit 4 by spontaneous expectoration over no more than 5 minutes and transported on ice for rapid processing (collection to storage within 30 minutes). Whole sputum will be immediately frozen at -20°C and then transferred to -80°C for storage prior to analysis (Horsley et al, 2014).

Rheological analysis will be performed before and after incubation at 37°C for 60 minutes (Horsley et al, 2014). Inflammatory mediators (IL-8, TNF- α and MPO) will be measured according to the published methodology (Downey et al, 2007).

Results will be provided to the Investigator for entry into the CRF.

7.2.3 Exhaled breath pH

Exhaled breath pH (UK centre only) will be measured pre-dose and at 8 and 24 hours post dose at Visit 2 to Visit 4. Exhaled breath pH measurement will be performed in accordance with the method described by MacNee et al, 2011. In brief, exhaled breath condensate (EBC) samples will be collected during tidal breathing for 10 minutes, without nose clips, using the RTubeTM (Respiratory Research Inc, Charlottesville, Virginia). A 200 μ L aliquot of EBC will be used for the pH assay. Measurement of pH will be performed after de-aeration by bubbling argon through the sample at 2 L/min while monitoring pH until the reading stabilised, usually after 8 minutes of de-aeration with argon.

7.3 Pharmacokinetic Assessments

Pharmacokinetic analysis will be performed on samples taken from all subjects. 4 mL blood samples will be collected at the following timepoints at Visit 2 to Visit 4: pre-dose, 15 and 30 minutes and 1, 2, 4, 6, 8 and 24 hours post-dose. Samples will be collected by venepuncture or via indwelling cannula in the forearm into lithium heparin tubes and will be immediately chilled (ice bath). The blood will be centrifuged within 30 minutes of collection. The plasma will be separated in a refrigerated centrifuge (about 4°C) at 1100g for 15 minutes and transferred into polypropylene tubes. After each blood collection, the plasma will be dispensed into two aliquots. After appropriate labelling, the plasma samples will be stored at, or below -20°C. The plasma samples will then be transported in dry ice to the central laboratory where they will be stored at or below -20°C until they are analysed using a validated method.

7.4 Safety Assessments

7.4.1 Adverse Events

Recording and reporting adverse events is described in detail in Section 8.

7.4.2 Laboratory Safety Assessments

All female patients will have a urine pregnancy test at screening (Visit 1), pre-dose at Visit 2 to Visit 4 and at the end of study visit (Visit 5) according to the study centre's standard operating procedures (SOPs).

All other laboratory safety assessments will be performed at each study centre's local laboratory. Samples will be handled and analysed according to the study centre and local laboratory standard procedures.

Monovette-S® (Sarstedt) tubes will be used to collect safety laboratory blood samples. Two samples will be collected at each timepoint, one sample for haematology using a 2.6 mL ethylenediaminetetraacetic acid (EDTA) whole blood collection tube and one 4.7 mL sample for biochemistry using a serum tube. A midstream urine sample will also be collected in a sterile container.

Samples will be taken at screening (Visit 1) and end of study visit (Visit 5) and analysed for:

Haematology: haemoglobin, haematocrit, total white cell count, leukocyte differential count and platelet count

Biochemistry: creatinine, total bilirubin, alkaline phosphatase, alanine transaminase, gamma-GT, potassium, sodium, urea

Urinalysis: leukocytes, blood, ketones, bilirubin, urobilinogen, protein and glucose using a dipstick. In the event of an abnormal dipstick urinalysis result, microscopic urinalysis may be conducted.

In addition, unscheduled and/or repeat testing may be performed at the discretion of the Investigator. Laboratory results will be provided to the Investigator for each patient and each visit. The Investigator should assign whether each abnormal result is not clinically significant or a clinically significant.

7.4.3 Vital Signs

Blood pressure and pulse rate will be measured at screening (Visit 1) and pre-dose, 30 minutes and 1, 2, 4, 6 and 8 hours post-dose at Visit 2 to Visit 4.

At each timepoint, supine vital signs will be assessed while the patient has been at rest for at least 5 minutes.

7.4.4 Physical Examination

A full physical examination, covering major body systems (assessments of the nose, throat, skin, thyroid gland, neurological system, respiratory system, cardiovascular system, abdomen [liver and spleen], lymph nodes and extremities) will be performed at screening (Visit 1). Results will be recorded in the CRF as normal, abnormal not clinically significant or abnormal clinically significant. The physical examination will be repeated at the end of study visit (Visit 5), and any changes only recorded.

7.4.5 12-Lead ECG

12-lead ECGs will be taken at screening (Visit 1) and pre-dose and 1, 2, 4 and 8 hours post-dose at Visit 2 to Visit 4.

At each timepoint, 12-lead ECGs should be taken after at least 5 minutes in the supine position. An ECG print out must be taken at each timepoint and signed and dated by the Investigator. An overall assessment (normal, abnormal not clinically significant or abnormal clinically significant) and continuous variables, including QT, heart rate and QTcF (or RR to derive QTcF) will be recorded in the CRF.

7.5 Blood Sampling

The maximum volume of blood taken from any subject during the study which includes laboratory safety tests and pharmacokinetic samples will be up to approximately 200 mL, allowing for any repeat sampling required.

7.6 Appropriateness of Measurements

The assessments planned in this study are recognised as reliable, accurate and relevant.

Plasma concentrations of RPL554 will be evaluated using a validated assay and quality control samples will be analysed throughout the study. The concentrations will be used to determine within run, between run and overall precision and accuracy of the method. The procedures, including the limits of quantitation and results will be described in detail in a separate bioanalytical protocol and report. The timing of pharmacokinetic samples is deemed appropriate to establish the exposure of patients to single doses of study treatment.

Spirometry is a standard lung function test used to screen for, and monitor, respiratory disease. Spirometry and daily calibrations will be performed in accordance with ATS/ERS task force standardisation guidelines (Miller et al, 2005) using the study centre's standard spirometry equipment and SOPs.

The measurement of sputum inflammatory mediators and exhaled breath pH will be performed in accordance with SOPs in place at Addenbrookes and Papworth Hospitals respectively.

Physical examinations, vital signs, 12-lead ECGs, adverse event recording and laboratory safety tests are standard assessments of safety and tolerability. The range of assessments to be performed is deemed appropriate to detect any safety signals.

8 HANDLING OF ADVERSE EVENTS AND PREGNANCIES

8.1 Adverse Event Definitions

Adverse event is defined as any undesirable experience occurring to a patient, or worsening in a patient, during a clinical study, whether or not considered related to the study treatment. An adverse event may be any of the following:

- A new illness
- An exacerbation of a sign or symptom of the underlying condition under treatment or of a concomitant illness
- Unrelated to participation in the clinical study or an effect of the study drug

- A combination of one or more of the above factors

No causal relationship with the study treatment is implied by the use of the term “adverse event.” An exacerbation of a pre-existing condition or illness is defined as a more frequent occurrence or as an increase in the severity of the pre-existing condition or illness during the study. Planned or elective surgical or invasive procedures for pre-existing conditions that have not worsened are not adverse events. However, any complication that occurs during a planned or elective surgery is an adverse event (if the event fits the serious criteria, such as an extended hospitalisation, it will be considered to be serious). Conditions leading to unplanned surgical procedures may be adverse events.

Adverse reaction is defined as all untoward and unintended responses to study treatment related to any dose administered.

Serious adverse event (SAE) is any adverse experience that:

- Results in death
- Is life-threatening
- Requires inpatient hospitalisation or prolongation of existing hospitalisation
- Results in persistent or significant disability/incapacity, OR
- Is a congenital anomaly/birth defect
- Other medical events*

*Important medical events that may not be immediately life-threatening or result in death or hospitalisation may be considered a SAE when, based on appropriate medical judgement, they may jeopardise the patient or may require medical or surgical intervention to prevent one of the outcomes listed above.

An unexpected adverse reaction is an adverse reaction in which the nature or severity of which is not consistent with the Investigator Brochure.

Suspected unexpected serious adverse reactions (SUSAR) is any suspected adverse reaction related to the study drug that is both unexpected and serious.

8.2 Recording and Assessing Adverse Events

All adverse events, whether reported spontaneously by the patient, in response to open questioning on treatment days or observed by the Investigator or his/her staff, will be recorded from informed consent until the end of study visit (Visit 5).

The start and stop time will be recorded and adverse events will be assessed by the Investigator for the following:

8.2.1 Severity

Mild: Resolved without treatment

Moderate: Resolved or was tolerated with specific treatment without affecting study activities

Severe: Did not resolve or was not tolerated with treatment

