8.2.2 Chronicity

Single occasion:	Single event with limited duration
Intermittent:	Several episodes of an event, each of limited duration
Persistent:	Event which remained indefinitely

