8.2.4 Action and Outcome

- Action taken with study treatment (none, study treatment stopped, study treatment temporarily interrupted)
- Other actions (none, concomitant medication, study discontinuation, hospitalisation, other)
- The outcome and date of outcome according to the following definitions:
 - Recovered or resolved (adverse event disappeared)
 - Recovering or resolving (patient is recovering)
 - Not recovered or not resolved (adverse event remains without signs of improvement)
 - Recovered or resolved with sequelae (adverse event has resulted in permanent disability or incapacity)
 - Fatal
 - Unknown (only applicable if patient has been lost to follow-up)
- Seriousness (yes or no)

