6.4.7 Safety Analysis

6.4.7.1 Adverse Events

Adverse events (AEs) will be collected throughout the study and will be coded according to the current version of the MedDRA dictionary. A treatment-emergent adverse event (TEAE) is defined as an AE that started or worsened after intake of study treatment in each treatment period. If the start date is unknown then the AE will be assumed to be treatment emergent unless the partial start date, or other data (i.e. stop date) indicates differently. The TEAEs will be assigned to the treatment given prior to onset of the event. In summaries, causally related AEs will consist of AEs classified as Unlikely, Probably or Definitely related to study treatment.

Coded adverse event terms will be presented by system organ class (SOC) and preferred term and summarised by treatment group. A summary table by treatment group with total number and number of patients with adverse events, SAEs, adverse events leading to discontinuation of study treatment, causally related adverse events and severe adverse events will be produced. Further SAEs, causally related adverse events and adverse events of each intensity will be summarised by SOC and preferred term.

AEs will be presented in decreasing frequency of the total number of patients with TEAEs. All AEs, including those which are not treatment emergent, will be listed. If appropriate, SAEs and AEs leading to discontinuation of study treatment will also be separately listed.

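### Protocol 8.2.1 grades adverse event severity by treatment and resolution instead of intensity, so the planned severity tables will not show what their titles say

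*Protocol*

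**What the plan says.** Protocol 8.2.1 gives the only severity definitions in the two documents:

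- The lowest grade reads "Mild: Resolved without treatment", with no term for intensity.
- The middle grade reads "Moderate: Resolved or was tolerated with specific treatment without affecting study activities", which brings in tolerance and study conduct.
- The highest grade covers an event that "Did not resolve or was not tolerated with treatment", again with no term for intensity.

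Other sections record neighbouring attributes in their own fields. Section 8.2.2 records chronicity, where a persistent event is an "Event which remained indefinitely". Section 8.2.4 records actions taken (including concomitant medication), outcome (including a category for events that have not resolved) and seriousness.

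SAP 4.5.1 lists the labels mild, moderate and severe without defining them, so the Protocol wording governs. SAP 6.4.7.1 plans an overview by treatment group in which counts of "causally related adverse events and severe adverse events will be produced", together with tabulations by intensity. The Protocol (Synopsis and 10.4.7) plans the same. In SAP 8.1, Table 14.3.1.4 is titled as a summary of events of moderate or severe intensity.

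**The concern.** A severity grade is meant to say how bad an event was. These definitions mostly say what was done about it and whether it went away. Tolerance appears under moderate and severe, and effect on study activities appears under moderate, so clinical impact is not wholly absent. It does not decide the grade for an event that was never treated.

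Tolerability and safety form a secondary objective (Protocol 2.2), and the split by severity is one of the ways the study will describe them. If the grades do not measure intensity, a reader who compares severe events between 1.5 mg, 6 mg and placebo is comparing something else. If the grades overlap or leave gaps, two investigators can grade the same event differently and both be following the Protocol.

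The Protocol also sits awkwardly with its own scale. Section 4.3.1 lists persistent events among the reasons for discontinuing treatment and allows them to be of any severity. On the plain reading of 8.2.1, an untreated event that persists can only be severe.

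**Working it through.** The plan states no figure to reproduce, so the check is logical: do the three definitions give each event one grade, and does that grade track intensity?

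**Inputs, all from Protocol 8.2.1.** Four yes/no attributes appear in the definitions: treated, resolved, tolerated, and affecting study activities. They give 2 × 2 × 2 × 2 = 16 combinations.

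**Rules applied**

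- Mild = resolved and not treated.
- Moderate = treated, and (resolved or tolerated), and not affecting study activities.
- Severe, reading A (plain): not resolved, or treated and not tolerated.
- Severe, reading B (the words about treatment qualify both limbs): treated, and (not resolved or not tolerated).

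**Result** (number of combinations in brackets)

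| Treated | Resolved | Tolerated | Affects study activities | Reading A | Reading B |
|---|---|---|---|---|---|
| no | yes | either | either | mild (4) | mild (4) |
| no | no | either | either | severe (4) | no grade (4) |
| yes | yes | yes | no | moderate (1) | moderate (1) |
| yes | yes | yes | yes | no grade (1) | no grade (1) |
| yes | yes | no | no | moderate and severe (1) | moderate and severe (1) |
| yes | yes | no | yes | severe (1) | severe (1) |
| yes | no | yes | no | moderate and severe (1) | moderate and severe (1) |
| yes | no | yes | yes | severe (1) | severe (1) |
| yes | no | no | either | severe (2) | severe (2) |

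- Reading A: exactly one grade in 4 mild + 1 moderate + 8 severe = 13 of 16; two grades in 2; no grade in 1.
- Reading B: exactly one grade in 4 mild + 1 moderate + 4 severe = 9 of 16; two grades in 2; no grade in 1 + 4 = 5.

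**What the table shows**

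1. On both readings, an untreated event that resolves is mild even if it was not tolerated and disrupted study activities.
2. An untreated ongoing event that was tolerated and affected nothing is severe on reading A and has no grade on reading B.
3. On both readings, a treated, tolerated, unresolved event that does not affect study activities is both moderate and severe.
4. On both readings, a treated, tolerated, resolved event that affects study activities has no grade.

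**Sensitivity to the moderate rule.** The proviso about study activities is taken to cover both limbs of moderate. If it covers only the tolerated limb, the gap in item 4 closes, because that event becomes moderate. The treated, resolved, not tolerated event that affects study activities then becomes both moderate and severe. One gap is exchanged for one overlap, and the totals with exactly one grade stay at 13 and 9.

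**Duplication.** Non-resolution contributes to three fields: severity (8.2.1), chronicity (8.2.2) and outcome (8.2.4). SAP Table 14.3.1.5 already tabulates intermittent or persistent events. No field records intensity alone.

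**The case against.** The strongest reply is that little depends on the grade. All adverse events are recorded whatever their grade (Protocol 8.2), tabulated by system organ class and preferred term (SAP 6.4.7.1, Table 14.3.1.2) and listed individually (Listing 16.2.7.1). Seriousness has its own definition, field, table and listing. Vital signs are taken at six post-dose times and ECGs at four, with their own change-from-baseline and shift summaries. No hypothesis test is planned on severity. Chronicity, outcome and action fields let a reader recover much of the context. All of this stands, and it limits the point to the severity split. It does not rescue that split, because none of those fields says how intense an event was.

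A reader might infer several stronger conclusions that the documents do not support:

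- *Every unresolved event is severe.* A treated, tolerated, unresolved event that leaves study activities unaffected also meets moderate, and on reading B an untreated one has no grade.
- *A serious event can be concealed as mild.* Seriousness is judged and reported separately from severity, so a serious event would still appear in Table 14.3.2.1 whatever its grade.
- *Acute reactions to the dose would be hidden.* They would be counted and listed; only their grade would be uninformative. A heart rate change at a scheduled time would also appear in the vital sign and ECG summaries. Protocol 1.2 reports palpitations at 24 mg and heart rate increases at 12 mg to 24 mg, above the doses used here.
- *Ordinary cystic fibrosis symptoms would inflate the severe count.* Under Protocol 8.1 a pre-existing condition is an adverse event only if it becomes more frequent or worse, and patients must be clinically stable for 2 weeks before randomisation. Being present at Visit 5 does not settle the matter either, since events are followed until abated or stable (8.3). The documents give no rate for such inflation.

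**Conclusion.** The point holds for the severity split only. The severe event count, the summaries by intensity and Table 14.3.1.4 would be labelled as intensity but driven mainly by treatment and resolution. The scale neither covers all cases nor separates them: 3 of 16 combinations lack a unique grade on the plain reading (16 − 13) and 7 of 16 on the alternative (16 − 9). These are counts of logical cases, not predictions of how many events will be misgraded; the documents give no basis for such a prediction.

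To illustrate sensitivity, with about 10 patients per treatment, one patient moved into or out of the severe row changes that proportion by 1/10 = 10 percentage points, provided that patient has no other severe event on that treatment. This would be true of any misclassification in a study of this size and is not an estimate of bias.

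The conclusion assumes that investigators grade from the Protocol wording and that no separate completion guidance overrides it; neither document mentions any that does. The primary pharmacokinetic endpoint is untouched. The point is worth correcting because a stated rule distorts part of a secondary tolerability outcome and the correction is simple.

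**What to change.** Replace the three definitions in Protocol 8.2.1 with intensity definitions that are mutually exclusive, cover every event and refer to neither treatment nor resolution. Degree of interference with the patient's usual activities is one workable basis; other intensity conventions would serve. Leave treatment given, outcome and chronicity in the fields that 8.2.2 and 8.2.4 already provide. Align the case report form completion guidance, and preferably repeat the definitions in SAP 4.5.1 so that the tables and the grades share one source. The SAP table shells need no change. With these definitions, the reference in 4.3.1 to persistent events of any severity would no longer conflict with 8.2.1.

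Merely closing the gap and the overlaps between the existing grades would make grading reproducible, but the result would still not measure intensity.

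The cost is three lines of text plus guidance, a protocol amendment with whatever approval Protocol 11.2 requires if it is judged substantial, and reduced comparability with any earlier study that used the present scale. If events have already been graded, intensity cannot be rebuilt from the outcome and treatment fields. Those events would need regrading from source notes, or the clinical study report should state which definitions applied.
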